7.6. Secondary Analysis Methodology

7.6.1. Safety of Fresh Start

From the safety parameters established in 6.3.1, safety of Fresh Start is to be assessed via the following over 6 months:

- Number of deaths

Number of deaths is to be presented by frequency per group.

- Number of emergency department admissions

Number of patients with emergency admissions is to be presented by frequency per group

- Number of hospital admissions

Frequency of events per patient is to be presented in a frequency table by treatment group with percentages to 1 dp.

Number of patients with hospital admissions is to be presented by frequency per group

Statistical comparison of safety will consist of a composite outcome, including all three events listed above. Number of patients with a safety event occurring is to be presented by frequency per group with difference in number of patients presented with a 95% CI.

7.6.2. Impact of Fresh Start on clinical outcomes.

From the clinical outcome parameters established in 6.3.2, potential efficacy of Fresh Start is to be assessed via the following

- **HbA1c, at baseline, 12-week and at 6 months**
- **Lipids, at baseline, 12-week and at 6 months**
- **Weight, at baseline, 12-week and at 6 months**

Tables displaying summary statistics will be produced displaying mean, SD, median, minimum & maximum at timepoints BL, W12 & M6

Within-group change from baseline at 12 weeks will be assessed via a mixed-effects model taking values at 12-weeks as the dependant variable and adjusting for covariates; baseline, sex, age, social deprivation index and allowing for clustering by GP Practice

Between-group differences in change from baseline at 12 weeks will be analysed using a similar mixed-effects model including an additional parameter for treatment effect and again adjusting for covariates; baseline, sex, age, social deprivation index and allowing for clustering by GP Practice

Further analysis will take place once long-term (6-month) follow-up is completed using an adjusted version of the above models containing additional terms for visit and visit*treatment interaction.

- **Diabetes Distress Scale score (DDS), as recorded within HUMA once monthly across the 12-week assessment period and also at 6 months**

Summary statistics displaying mean, SD, median, minimum & maximum DDS will be produced at for first reading and last reading.

Within-group change from first DDS score to last DDS score will be assessed via a mixed-effects model taking DDS Score as dependant variable and adjusting for covariates; study day (of reading), sex, age, social deprivation index and allowing for clustering by GP Practice

- **Blood glucose time-in-range, as recorded within HUMA over the 12-week assessment period**

Investigating difference between means of days in-range after 12-weeks will be analysed using mixed-effects model adjusting for covariates; sex, age, social deprivation index and allowing for clustering by GP Practice.

The above analysis is dependent on a suitable number of data points being collected per patient to assess time-in-range. If this analysis is deemed not feasible. Change in blood glucose will be presented using the same method as for HbA1c, Lipids & Weight. First blood glucose reading will be taken as baseline per patient.

Summary statistics displaying mean, SD, median, minimum & maximum blood glucose will be produced at for first reading and last reading.

- **Systolic blood pressure (SBP), as recorded within HUMA, as recorded within HUMA over the 12-week assessment period**

Summary statistics displaying mean, SD, median, minimum & maximum blood glucose will be produced at for first reading and last reading.

Investigating difference between means of SBP after 12-weeks will be analysed using mixed-effects model adjusting for covariates; sex, age, social deprivation index and allowing for clustering by GP Practice

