5.1 Definitions

Adverse Event (AE): any untoward medical occurrence in a patient or clinical study subject.

Serious Adverse Event (SAE): any untoward and unexpected medical occurrence or effect that:

- **Results in death**

- **Is life-threatening** – refers to an event in which the subject was at risk of death at the time of the event; it does not refer to an event which hypothetically might have caused death if it were more severe
- **Requires hospitalisation, or prolongation of existing inpatients' hospitalisation**
- **Results in persistent or significant disability or incapacity**
- **Is a congenital anomaly or birth defect**

Medical judgement should be exercised in deciding whether an AE is serious in other situations. Important AEs that are not immediately life-threatening or do not result in death or hospitalisation but may jeopardise the subject or may require intervention to prevent one of the other outcomes listed in the definition above, should also be considered serious.

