5.2 Reporting procedures

All adverse events should be reported. Depending on the nature of the event the reporting procedures below should be followed. Any questions concerning adverse event reporting should be directed to the Chief Investigator in the first instance.

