5.2.1 Non serious AEs

All such events, whether expected or not, should be recorded- it should be specified if only some non-serious AEs will be recorded, any reporting should be consistent with the purpose of trial end points.

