5.2.2 Serious AEs

An SAE form should be completed and emailed to the Chief Investigator within 24 hours. However, hospitalisations for elective treatment of a pre-existing condition do not need reporting as SAEs.

All SAEs should be reported to the Bromley Research Ethics Committee ([contact]) where in the opinion of the Chief Investigator, the event was:

- 'related', ie resulted from the administration of any of the research procedures; and
- 'unexpected', i.e., an event that is not listed in the protocol as an expected occurrence

Reports of related and unexpected SAEs should be submitted within 15 days of the Chief Investigator becoming aware of the event, using the NRES SAE form for non-IMP studies. The Chief Investigator must also notify the Sponsor of all SAEs.

Local investigators should report any SAEs as required by their Local Research Ethics Committee, Sponsor and/or Research & Development Office.

Contact details for reporting SAEs

[contact]

CI email (and contact details below)

Please send SAE forms to: [contact] and Cc [contact]

[contact] (Mon to Fri 09.00 – 17.00)

6. Regulatory issues

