7.7. Exploratory / Sub-group Analysis

For outcome measures defined in section 6.2, analysis may be repeated, breaking down the results into two separate sub-groups.

One potential classification relates to those enrolled who were able to strictly adhere to the FreshStart treatment protocol (including remote monitoring) and will be compared against those that were unable to adhere but were still able to participate in some manner (i.e take part in VGCs).

Additional sub-groups may be determined during the course of analysis and treated as post-hoc analysis.

Additional exploratory analysis may also be carried out for collected data not assessed in the above primary & secondary outcomes.

8. Missing Data

As a feasibility study, part of the feasibility assessment is to establish the extent of missing data. In the event where data in the propensity-matched control arm is missing it may be appropriate that replacement patients may be considered on the basis that they are still within suitable parameters of the matching algorithm and balancing remains unaffected.

9. SAP Revisions

Version	Date	Details
0.1	13MAY2022	Final Draft prior to signing off
0.2	11JULY2022	Removing definition of benchmark for time-in-range comparison (to be added post-hoc once a suitable reference point is found).

Appendix 1

Summary of Tables, Figures & Listings

Reference	Title	Template
1.1	CONSORT Diagram	N/A
2.1	Demographics – Treatment & Control	1
2.2	Demographics – HUMA Users vs Non-Users in Treatment Arm	1
3.1	Uptake - offered Fresh Start vs. enrolled	N/A
3.2	Uptake - enrolled vs. collecting devices	N/A
4.1	Usability - VGCs attended	2
4.2	Usability - blood glucose measurements recorded	2
4.3	Usability - blood pressure measurements recorded	2
4.4	Usability - weight measurements recorded	2
4.5	Usability - Diabetes Distress Scale measurements recorded	2
5.1.1-2	Costings - Primary care appointments per patient	2 & 5
5.2.1-2	Costings - Cost per appointment per patient	3 & 5
5.3	Costings - Cost of equipment per patient	3
6.1	Safety - Number of deaths	6
6.2	Safety - Number of emergency department admissions	6
6.3	Safety - Number of hospital admissions	6
7.1.1-2	Clinical – HbA1c Within Groups	3 & 5
7.1.3-2	Clinical – HbA1c Between Groups	4 & 5
7.2.1-2	Clinical – Lipids, incl. LDL and non-HDL cholesterol Within Groups	3 & 5
7.2.3-2	Clinical – Lipids, incl. LDL and non-HDL cholesterol Between Groups	4 & 5
7.3.1-2	Clinical – Weight (or BMI as appropriate) Within Groups	3 & 5

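### The adverse event and SAE data that the protocol requires, including the judgement of relatedness, have no committed place in the safety analysis, which rests only on all-cause deaths, ED admissions and hospital admissions

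*SAP*

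**What the plan says.** **What is collected.** Protocol 5.2 opens with "All adverse events should be reported". For non-serious events, 5.2.1 says "All such events, whether expected or not, should be recorded- it should be specified if only some non-serious AEs will be recorded", and the sentence ends by asking that reporting fit the purpose of the end points. For serious events, 5.2.2 says "An SAE form should be completed and emailed to the Chief Investigator within 24 hours". The Chief Investigator gives an opinion on whether the event was related to the research procedures and unexpected, and must tell the sponsor of every SAE. For the ethics committee, "Reports of related and unexpected SAEs should be submitted within 15 days of the Chief Investigator becoming aware of the event". The definition in 5.1 goes beyond death and hospital stay: it adds life-threatening events, lasting disability, congenital anomaly and "Important AEs that are not immediately life-threatening or do not result in death or hospitalisation but may jeopardise the subject".

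**What is analysed.** Protocol 3.6 lists three safety measures: deaths (EPR), emergency department admissions (WSIC) and hospital admissions (WSIC). SAP 6.1, 6.3.1 and 7.2 repeat them. SAP 7.6.1 begins "From the safety parameters established in 6.3.1, safety of Fresh Start is to be assessed via the following over 6 months", lists the same three and adds a composite for the statistical comparison. The safety entries in SAP Appendix 1 are tables 6.1 to 6.3, the last being "Safety - Number of hospital admissions". SAP 7.7 allows optional exploratory work on other collected data and does not name adverse events.

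**The concern.** Safety is part of the study aim and a named secondary objective. The protocol sets up one data source that records events as harms and asks whether the service caused them, and no planned output draws on it. The three routine-data counts are all-cause. They cannot show whether an admission had anything to do with Fresh Start, and they do not register a serious event managed without admission. The service can lead to medication review, care-plan changes and escalation of urgent readings (Protocol 3.4 and 3.7), and harm from such steps need not end in hospital. A conclusion about safety would therefore be drawn without the study's own safety reports.

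**Working it through.** The plan states no figure for this point, so the check sets the sections side by side.

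**Step 1: source of each planned safety measure** (Protocol 3.6; SAP 6.1, 6.3.1, 7.6.1). Deaths come from the EPR, and both kinds of admission from WSIC. Measures drawn from AE or SAE records: 0 of 3. The composite is built from the same three.

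**Step 2: planned output** (SAP Appendix 1). Tables 6.1, 6.2 and 6.3 cover deaths, emergency department admissions and hospital admissions. Safety tables showing AEs, SAEs, seriousness or relatedness: 0 of 3. No AE or SAE listing is planned.

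**Step 3: Protocol section 5 against the planned output.**

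| Protocol section 5 item | Place in planned safety output |
|---|---|
| Death | Counted, from the EPR |
| Hospitalisation | Counted, from WSIC; a prolonged stay is not a new admission |
| Life-threatening event | Only if it also leads to death or an admission |
| Persistent disability or incapacity | As above |
| Congenital anomaly | As above |
| Medically important event | As above |
| Relatedness and expectedness of SAEs | None |
| Non-serious AEs | None, unless the patient has an emergency department or hospital admission |

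Section 5.1 gives six routes to seriousness: five listed criteria and the medical-judgement route. Two match a planned count. The other 6 − 2 = 4 are visible only when they coincide with death or an admission.

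**Step 4: can admission counts stand in for SAEs?** No. Protocol 5.2.2 exempts elective admission for a pre-existing condition from SAE reporting, and SAP 7.6.1 states no matching exclusion. The admission count can therefore exceed the SAE count for that reason, and fall short of it for the four routes above.

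**Step 5: safety window.** SAP 6.3.1 sets the safety variables over the 12-week period. SAP 7.2 and 7.6.1 use 6 months. Any added table would inherit this conflict.

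**Step 6: what the records can support.** The relatedness and expectedness opinion is asked for SAEs only (Protocol 5.2.2), so non-serious AEs can only be counted. Which of them are recorded is unsettled, because 5.2.1 first says all and then carries what reads as an uncompleted template instruction. Controls come from WSIC with no AE reporting described, so no between-group comparison is possible.

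**The case against.** **The SAP follows the protocol's outcome table.** This stands. Protocol 3.6 names the same three measures, so a reader who infers that the SAP deviates from the protocol's listed outcomes is mistaken. The mismatch is between Protocol section 5 and both outcome lists.

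**SAEs are reported.** A reader might infer that harms short of admission, and every relatedness judgement, are lost. The documents do not support that. All SAEs go to the Chief Investigator and the sponsor, and related and unexpected ones to the ethics committee. Case-by-case reporting is not a study-level summary, however, and only the summary is missing.

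**Other outcomes would show harm.** In part. Glucose, systolic pressure and the distress score are summarised (SAP 7.6.2), and reasons for withdrawal are recorded (Protocol 4.5). But time-in-range combines readings below and above the 70 to 180 mg/dl band, and none of these outputs identifies an adverse event or its cause.

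**SAP 7.7 leaves room, and the objective is exploratory.** An optional clause is not a commitment. A descriptive table needs no power and no test.

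**A table could falsely reassure.** This stands. With no related SAE among 300 participants, the one-sided 95% upper limit would be 1 − 0.05^(1/300) = 0.99%. It is tempting to read that as a demonstrated ceiling. It would hold only with complete ascertainment and no clustering by practice. The staff actions in Protocol 3.7 and the follow-up measures in 3.9 include no routine AE enquiry.

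**The data may not reach the analysts.** This stands as a cost. SAE forms are emailed to the Chief Investigator, while the research team works on de-identified data in the WSIC environment (Protocol 3.11 and 3.12).

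**Conclusion.** The concern holds as a gap in planned analysis. The protocol requires AE and SAE reports, with a judgement of relatedness and expectedness for SAEs, and neither document commits to summarising them. Its size is structural: 0 of 3 safety measures and 0 of 3 safety tables use these records, and 4 of the 6 routes to seriousness are seen only when they coincide with death or an admission. The number of patients affected cannot be given, because the documents state no AE rate. As planned, the safety objective would be answered without attribution and without serious events managed outside hospital.

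This rests on two assumptions: that the study dataset named in SAP 6.3.1 does not already hold AE or SAE records (no section describes it doing so), and that SAE forms are completed as Protocol 5.2.2 requires.

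**What to change.** - **SAP 6.3.1, 7.6.1 and Appendix 1:** add one descriptive table for the Fresh Start group. For SAEs, give the number and percentage of patients and the number of events, by seriousness criterion, relatedness and expectedness. For whichever non-serious AEs are recorded, give counts only.
- **Data route:** state that the table is supplied as de-identified or aggregate counts from the SAE forms, in keeping with Protocol 3.11.
- **Interpretation:** state that there is no control comparison, that events are ascertained by passive report, and that no confidence bound is to be read as proof of safety.
- **Safety window:** reconcile SAP 6.3.1 with 7.2 and 7.6.1, and apply the agreed window to this table.
- **Protocol 5.2.1:** complete the template sentence so that the non-serious AEs recorded are those tabulated. Which events these are is for the investigators to decide.

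The cost is SAP wording, one table and one corrected protocol sentence, plus a step for passing SAE counts from the Chief Investigator to the analysts, which the documents do not now describe. The drawback is that the table has no comparator.

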7.7. Exploratory / Sub-group Analysis

For outcome measures defined in section 6.2, analysis may be repeated, breaking down the results into two separate sub-groups.

One potential classification relates to those enrolled who were able to strictly adhere to the FreshStart treatment protocol (including remote monitoring) and will be compared against those that were unable to adhere but were still able to participate in some manner (i.e take part in VGCs).

Additional sub-groups may be determined during the course of analysis and treated as post-hoc analysis.

Additional exploratory analysis may also be carried out for collected data not assessed in the above primary & secondary outcomes.

8. Missing Data

As a feasibility study, part of the feasibility assessment is to establish the extent of missing data. In the event where data in the propensity-matched control arm is missing it may be appropriate that replacement patients may be considered on the basis that they are still within suitable parameters of the matching algorithm and balancing remains unaffected.

9. SAP Revisions

Version	Date	Details
0.1	13MAY2022	Final Draft prior to signing off
0.2	11JULY2022	Removing definition of benchmark for time-in-range comparison (to be added post-hoc once a suitable reference point is found).

Appendix 1

Summary of Tables, Figures & Listings

Reference	Title	Template
1.1	CONSORT Diagram	N/A
2.1	Demographics – Treatment & Control	1
2.2	Demographics – HUMA Users vs Non-Users in Treatment Arm	1
3.1	Uptake - offered Fresh Start vs. enrolled	N/A
3.2	Uptake - enrolled vs. collecting devices	N/A
4.1	Usability - VGCs attended	2
4.2	Usability - blood glucose measurements recorded	2
4.3	Usability - blood pressure measurements recorded	2
4.4	Usability - weight measurements recorded	2
4.5	Usability - Diabetes Distress Scale measurements recorded	2
5.1.1-2	Costings - Primary care appointments per patient	2 & 5
5.2.1-2	Costings - Cost per appointment per patient	3 & 5
5.3	Costings - Cost of equipment per patient	3
6.1	Safety - Number of deaths	6
6.2	Safety - Number of emergency department admissions	6
6.3	Safety - Number of hospital admissions	6
7.1.1-2	Clinical – HbA1c Within Groups	3 & 5
7.1.3-2	Clinical – HbA1c Between Groups	4 & 5
7.2.1-2	Clinical – Lipids, incl. LDL and non-HDL cholesterol Within Groups	3 & 5
7.2.3-2	Clinical – Lipids, incl. LDL and non-HDL cholesterol Between Groups	4 & 5
7.3.1-2	Clinical – Weight (or BMI as appropriate) Within Groups	3 & 5
7.3.3-2	Clinical – Weight (or BMI as appropriate) Between Groups	4 & 5
7.4.1-2	Clinical – Diabetes Distress Scale score (DDS[iii]) Within Groups	3 & 5
7.4.3-2	Clinical – Diabetes Distress Scale score (DDS[iii]) Between Groups	4 & 5
7.5.1-2	Clinical – Blood glucose time-in-range Within Groups	3 & 5
7.5.3-2	Clinical – Blood glucose time-in-range Between Groups	4 & 5

Imperial Clinical Trials Unit	SUB-STUDY SAP TEMPLATE – SUB-ANALYSES AND OBSERVATIONAL STUDIES	SOP_TEM_BS002
-------------------------------	---	---------------

Appendix 2

Shell/Dummy Tables, Figures & Listings

Template 1: Demographics

Variable		Unit	Group X	Group Y
Age	Years	Mean (SD)		
	Years	Median [Q1 – Q3]		
Sex	Male	n(%)		
Ethnicity	Asian (inc. Asian British)	n(%)		
	...	n(%)		
	...	n(%)		
DI Deciles	1	n(%)		
	...	n(%)		
	...	n(%)		

Template 2: Descriptive (Summary) Statistics – Frequency Output

	n	Mean	SD	Median	Min	Max
Average no. Readings	xx	xx.x	xx.x	xx.x	xx.x	xx.x
Ave. Readings/Day	xx	xx.x	xx.x	xx.x	xx.x	xx.x

Template 3: Descriptive (Summary) Statistics – Within Groups

	n	Mean	SD	Median	Min	Max
First Value/ Baseline	XX	XX.X	XX.X	XX.X	XX.X	XX.X
Final Value	XX	XX.X	XX.X	XX.X	XX.X	XX.X
Δ	XX	XX.X	XX.X	XX.X	XX.X	XX.X

Template 4: Descriptive (Summary) Statistics – Between Groups/Sub-groups

	n	Mean	SD	Median	Min	Max
Δ Group x	XX	XX.X	XX.X	XX.X	XX.X	XX.X
Δ Group y	XX	XX.X	XX.X	XX.X	XX.X	XX.X
Δ between groups	XX	XX.X	XX.X	XX.X	XX.X	XX.X

Template 5: STATA Mixed-Model Output (example)

```

Mixed-effects ML regression
Group variable: id
Number of obs      =      432
Number of groups  =       48
Obs per group:
   min =          9
   avg =        9.0
   max =          9
Wald chi2(1)      =    25337.49
Prob > chi2       =     0.0000
Log likelihood = -1014.9268

      weight   Coefficient  Std. err.      z    P>|z|    [95% conf. interval]
      week      6.209896   .0390124   159.18   0.000    6.133433   6.286359
      _cons     19.35561   .5974059    32.40   0.000    18.18472   20.52651

      Random-effects parameters
      Estimate  Std. err.    [95% conf. interval]
      id: Identity
      var(_cons)  14.81751  3.124226    9.801716   22.40002
      var(Residual) 4.383264  .3163348   3.805112   5.04926

      LR test vs. linear model: chibar2(01) = 472.65      Prob >= chibar2 = 0.0000

```

Template 6: Frequency of Events Table & Chi-Sq Test (Example)

Repair Record 1978	Car type		Total
	Domestic	Foreign	
1	2	0	2
2	8	0	8
3	27	3	30
4	9	9	18
5	2	9	11
Total	48	21	69

Pearson chi2(4) = 27.2640 Pr = 0.000

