3.5 Matched control group

A number of the study's objectives and associated outcome measures will require a control group for comparison. These objectives include:

- To assess the cost-effectiveness of delivering Fresh Start;
- To assess the safety of Fresh Start; and
- To assess the impact of Fresh Start on clinical outcomes.

This study will create a matched control group using propensity score matching (PSM),⁹ a quasi-experimental method used to mimic the characteristics of a randomised control trial that has been shown to reduce biases.¹⁰ PSM uses statistical techniques to construct an artificial control group by matching each study participant with a non-treated participant of similar characteristics. PSM computes the probability that a person would enrol in a program based on pre-defined characteristics, giving a 'propensity score'.

The propensity score for the study will be based on the following characteristics:

- Age
- Gender
- Risk category (see inclusion criteria)
- Geographical proximity
- Social deprivation index (by practice)

Each individual in the matched control group will be identified within one month of the index case.

Imperial College London

The matched control group will be identified using NWL's Whole of Systems Integrated Care (WSIC) database. WSIC links provider data from four acute, two mental health and two community Trusts across eight CCGs, social care data from eight boroughs and 380 GP practices to generate an integrated care record.

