6.2.5. Cost-effectiveness of delivering Fresh Start

Cost-effectiveness is to be determined by the following measures:

- Number of primary care appointments per patient - as entered in study dataset over the 12-week assessment period
- Cost per appointment per patient - as entered in study dataset
- Cost of equipment per patient – defined below:

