7.1.2. Propensity Score Matching

For the primary cost-benefit comparison and secondary safety and efficacy comparisons, study data will be compared against a matched-control group established via propensity score matching. This is achieved by deriving a propensity score for each enrolled patient based on the following characteristics:

- Age
- Gender
- Geographical proximity
- Social deprivation index (by practice)

- Ethnicity

Using the above categories, taking 'arm' as the dependent variable, logistic regression using a generalised logit model will be used to generate the estimated propensity scores. Scores are also applied to a control 'arm' taken from the WSIC database as section 5.2.2 with everyone in the matched control identified within one month of the index case. The scores are then used to 'pair-up' patients within both groups, patients will be matched on a 1:1 basis without replacement.

Scores are to be calculated using PSOCORE in STATA. Matching is to be carried out using PSMATCH2 (or a suitable alternative). Balancing on matching variables is to be checked once matching is completed using PSTEST. If any variable is found to be unbalanced the matching is repeated, either adjusting the matching method or caliper used.

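### SAP section 8 lets matched controls with missing data be replaced without limiting this to data known at the index date, so control membership could come to depend on follow-up.

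*SAP*

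**What the plan says.** SAP section 8 (Missing Data) is the whole missing-data plan. It first notes that establishing the extent of missing data is part of the feasibility assessment. It then adds: "In the event where data in the propensity-matched control arm is missing it may be appropriate that replacement patients may be considered". The sentence attaches one condition, namely that a substitute must still fit the matching limits and must not upset balance. It does not say whether baseline or follow-up data are meant, how many replacements are allowed, or when they may be made. There is no matching rule for Fresh Start patients.

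SAP 7.1.2 defines the matching. The score uses age, gender, geographical proximity, practice deprivation and ethnicity, and "patients will be matched on a 1:1 basis without replacement". Balance is checked on those variables only. The same section has controls chosen "with everyone in the matched control identified within one month of the index case", as does Protocol 3.5.

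The control arm then serves several comparisons:
- Primary care appointments and their cost, under a primary objective (SAP 6.2.5 and 7.5.5): "Number of primary care appointments per patient - as entered in study dataset over the 12-week assessment period".
- Deaths, emergency admissions and hospital admissions (SAP 7.6.1): "Number of deaths is to be presented by frequency per group", plus a composite of all three with a 95% CI.
- HbA1c, lipids and weight from patient records at baseline, 12 weeks and 6 months (SAP 6.3.2).

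**The concern.** The two arms generate data differently. Fresh Start patients have booked baseline measurements and a formal 12-week review with HbA1c, lipids and weight (Protocol 3.7), and a month-6 appointment (Protocol 3.9). No equivalent visit is described for controls, who are drawn from the WSIC database. A control has a 12-week or 6-month value only if routine care happened to produce one.

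Replacing controls who lack that value selects the control arm on something that happens after the index date. Balance on age, gender, proximity, deprivation and ethnicity cannot reveal this, because none of these measures attendance, morbidity or survival.

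The replacement also discards usable information. A control without an HbA1c still has appointments, costs, admissions and vital status that can be counted, up to death or leaving the practice. Swapping to rescue an exploratory outcome could therefore distort a primary one. It would also hide the extent of missing data, which section 8 itself sets out to establish.

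**Working it through.** The plan gives no figure on this point: no visit rate, dispersion, missingness or replacement fraction. The visit rates, spreads, recording probabilities and death risks below are assumptions. Only the 12-week and 6-month windows, the 1:1 ratio and the minimum of 300 participants come from the documents. There is no true group difference in any of the calculations.

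**1. Every control must have at least one contact in 12 weeks.** The mean given at least one contact is μ/(1−P(0)). For a Poisson count this is μ/(1−e^−μ). For a negative binomial with dispersion 1, P(0) = 1/(1+μ), which gives 1+μ.

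| True mean μ | Poisson | Negative binomial |
|---|---|---|
| 1.5 | 1.5/0.777 = 1.93 (+29%) | 2.5 (+67%) |
| 3.0 | 3.0/0.950 = 3.16 (+5%) | 4.0 (+33%) |

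**2. Each appointment yields a record with probability q.** A control with x visits has no record with probability (1−q)^x. Take μ = 2, dispersion 1 and q = 0.3.
- Share without a record: 1/(1 + 2×0.3) = 0.625.
- E[x·0.7^x] = 0.7×2/1.6² = 0.547. The mean is therefore 0.547/0.625 = 0.875 visits among the unrecorded and (2 − 0.547)/0.375 = 3.875 among the recorded.
- All missing controls swapped: control mean 3.875, Fresh Start/control ratio 2/3.875 = 0.52.
- Half swapped: 0.375×3.875 + 0.625×(0.5×3.875 + 0.5×0.875) = 2.94, ratio 0.68.
- A quarter swapped: 2.47, ratio 0.81.

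**3. Range, by simulation with all missing controls swapped.**
- Mean 1 to 3 visits, q from 0.1 to 0.5, gamma shape from 0.5 to no extra spread: ratio 0.28 to 0.87.
- 60% recorded whatever the attendance, with q = 0.3 for the rest (mean 1 to 3 visits, gamma shape 1 or 2): 0.83 to 0.89.
- Missingness unrelated to attendance: 1.00.

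**4. Longer window.** SAP 7.2 summarises appointments to 6 months, whereas 6.2.5 and 7.5.5 use 12 weeks. At 1.5 per 12 weeks, the 26-week mean is 1.5×26/12 = 3.25. In the Poisson case the excess stays at 0.43, and 0.43/3.25 is about +13%.

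**5. Swaps for missing baseline records only.** With mean 2, q = 0.3 and gamma shapes 0.5 to 2, the ratio is 0.47 to 0.75. Selection is then on attendance before the index date, which is not a matching variable.

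**6. Deaths.** With 300 controls at 1:1 and an assumed 6-month risk of 0.5% to 2%, expected deaths are 300×0.005 = 1.5 to 300×0.02 = 6. One replaced death is a visible part of that count.

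**The case against.** The sentence in section 8 is doubly hedged and names neither follow-up values nor deaths. A reader might infer that the rule will load the control arm with frequent attenders. The documents do not support that as a fact: it requires that swaps are made and that recording tracks attendance. What stands is that the wording does not rule it out.

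A reader might also infer that section 8 contradicts the one-month identification rule. It need not. That rule sits inside the matching procedure, and replacements must stay within the matching parameters, so it may already bind them and bar late swaps. The SAP does not say; this is an ambiguity.

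A third tempting inference is that safety is biased against Fresh Start because control deaths would be lost. Death is itself a recorded outcome, and nothing indicates that dead controls are meant to be replaced, although a missing 12-week value would permit it. The only planned statistical safety comparison is the composite. If replacements use more care, control admissions could rise and offset any lost deaths, so the net direction is undetermined.

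Nor do the illustrative figures measure the bias between arms. They are shifts from the controls first matched. Fresh Start patients are volunteers and prior attendance is unmatched, so part of the shift could be offset. The 6-month window dilutes the Poisson example to about +13%.

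Finally, this is a feasibility study, its safety and clinical outcomes are exploratory, and no decision threshold is attached to the cost objective. That limits the severity but does not make the rule sound.

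**Conclusion.** The point holds as a defect of scope. Section 8 permits replacement on data that arise after the index date, applies to one arm only, and has a safeguard that cannot detect the resulting selection. If it were used on missing 12-week or 6-month values, and recording depends on attendance, control appointments and costs would rise relative to the controls first matched. In the worked cases where every control must have a contact in 12 weeks, the rise is 5% to 67%. In the recording model, the null ratio lies between 0.28 and 0.89 when all missing controls are swapped. These figures show direction and sensitivity, not an estimate; the net between-arm bias is unknown. This should be fixed before follow-up data are extracted, but it does not invalidate the study.

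**What to change.** Reword SAP section 8 along these lines:
- Apply any requirement for matching or baseline data as an eligibility condition on the control pool before matching, using only data up to the index date.
- Lock the matched set before any follow-up data are extracted.
- Allow no replacement for missing follow-up values, death or de-registration.
- State how the one-month identification rule in Protocol 3.5 and SAP 7.1.2 applies to the locked set.
- Count appointments, costs and safety events for every locked pair.
- Analyse clinical outcomes with the planned mixed models on available data, and report missingness by arm.

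The SAP should also state two limits that remain. Available-data comparisons of HbA1c, lipids and weight are still selected on having been tested, since the 12-week model uses the 12-week value as its dependent variable. A baseline-data requirement may still favour prior attenders, as step 5 of the working shows; applying it before matching makes that selection explicit and independent of follow-up, but does not remove it.

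The change is to SAP wording only. Its price is fewer control values, and so wider intervals, on clinical outcomes already labelled exploratory.
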